18.3. Patient Termination

A study patient will be terminated if the study patient develops any severe adverse event that may be related to the study. A study patient will receive appropriate treatment at the discretion of the investigator. Notification of termination will be clearly documented. These study patients are considered to have completed the study and will not be replaced.

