9.2. Visits and Examinations

Subjects will participate in seven study visits, one eye per visit for bilateral surgery. Visits will include an uptake visit, two operative visits, and 5 total postoperative visits (Visit numbers 1-6 below). The visit schedule, complete with window and associated

CRF forms, are displayed in Table 9.2-1. Details of each study visit, including testing to be conducted, are provided below.

Table 9.2-1. Visit Schedule

Visit Number	Visit Name	Visit Window	CRF Number
1	Preoperative	-60 to 0 days from surgery	1
2,2a	Operative	0 from surgery	2,2a
3,3a	1 Day Postoperative	1-2 days postoperative*	3,3a
4	1 Week Postoperative	7 (± 2) days postoperative**	4
5	1 Month Postoperative	30 (± 10) days postoperative**	5
6	3 Months Postoperative	90 (± 20) days postoperative**	6

* relative to the operative eye

** relative to the date the last eye is operated on

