9.2.7. Exit Procedures

In the event of premature exit from the study, all study related examinations should be completed where possible. The Exit CRF should be completed, noting that the subject did not complete the study and the reason for premature study exit. If no premature exit from the study occurs, the Exit CRF should be completed at the end of Visit 6 (Postoperative 3 Months).

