9.5. Discontinued Subjects

Discontinued subjects are those who do not have an exit visit or who come into the office to be exited prior to the scheduled final study visit. Subjects may be discontinued from the study at any time if, in the opinion of the investigator, their continued participation in the study poses a risk to their health. The reasons for discontinuation include:

- a. Adverse event;
- b. Lost to follow-up;
- c. Subject decision unrelated to an adverse event;
- d. Protocol violation;
- e. Treatment failure;
- f. Other.

To ensure the safety of all subjects who discontinue prior to Visit 6, investigators should assess each subject and, if necessary, advise them of any therapies and/or medical procedures that might be needed to maintain their health. Any changes in medical health and/or use of concomitant medications should also be captured.

10. ANALYSIS PLAN***10.1. Analysis Data Sets***

All subjects who are enrolled in the study will be evaluated for safety. Efficacy analyses will be performed based on data from those eyes where uncomplicated cataract surgery with Vivity IOL implantation was completed.

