18. STUDY ENDPOINT CRITERIA

18.1. Patient Completion of Study

If a study patient has completed the final visit (Visit 6) of the study, he/she is considered to have completed the study.

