18.5. Study Completion

The study will be complete when all enrolled patients have completed Visit 6 or have been terminated from the study.

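### Section 18.3 terminates patients after any severe, possibly related adverse event, so one terminated before day 70 has no planned 3-month outcome and an unclear completion status

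*Combined protocol and SAP*

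**What the plan says.** Section 18.3 is mandatory: "A study patient will be terminated if the study patient develops any severe adverse event that may be related to the study". It makes no exception for collecting outcomes, and it adds: "These study patients are considered to have completed the study and will not be replaced".

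Section 18.5 treats termination as an alternative to the last visit: "The study will be complete when all enrolled patients have completed Visit 6 or have been terminated from the study".

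Table 9.2-1 sets Visit 6 at "90 (± 20) days postoperative", counted from surgery on the last eye. Table 15.1 schedules the binocular uncorrected and corrected acuities at all three distances, the low-contrast acuity and both questionnaires at that visit only; 9.3.3 confirms this for the questionnaires.

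On early exit, 9.2.7 says: "In the event of premature exit from the study, all study related examinations should be completed where possible".

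On completion, 18.1 says: "If a study patient has completed the final visit (Visit 6) of the study, he/she is considered to have completed the study". Section 9.5 includes among discontinued subjects those "who come into the office to be exited prior to the scheduled final study visit". For a premature exit, 9.2.7 says: "The Exit CRF should be completed, noting that the subject did not complete the study and the reason for premature study exit". Section 10.2 bases its summaries on eyes that complete the study.

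**The concern.** The lens is already in place when a postoperative event occurs, so terminating the patient withdraws no exposure. What it can remove is the 3-month outcome. Section 9.5 already lets the investigator discontinue anyone whose health would be at risk from continuing, so the mandatory rule adds little protection.

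The loss can depend on the outcome. An incapacitating visual symptom that may be due to the lens meets the trigger, and that patient's 3-month acuity and questionnaire answers are among those the study most needs. The study has one arm, 20 patients and no performance target, so the descriptive 3-month summaries are its result.

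Separately, the plan gives such a patient two opposite statuses. An analyst could treat early exit values as 3-month data, or drop the patient, and cite the protocol for either choice.

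**Working it through.** **Timing.** Visit 6 opens at 90 − 20 = day 70 and closes at 90 + 20 = day 110 after the second eye. Termination before day 70 precedes every scheduled binocular test and both questionnaires. Termination inside the window does little harm, because the exit examination then falls within it.

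**What remains after early termination.**
- 9.2.7: exit examinations if feasible. These could include the binocular tests and questionnaires, but at the exit date.
- Table 15.1: acuity and refraction at 1 week and 1 month, with acuity monocular only.
- 13.4: medical follow-up, with data that may be added to the CRFs.

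None of these is a planned 3-month binocular or questionnaire value. Section 10 has no rule for missing data.

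**Completion status of the same patient.**

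| Section | Status |
|---|---|
| 18.3 | completed |
| 18.1 | completed only if Visit 6 was done |
| 9.5 | discontinued |
| 9.2.7 | Exit CRF records non-completion |

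**The plan's own precision figure.** Section 11 gives n = 20, SD 0.1 logMAR and a t-based 95% interval extending 0.05. Half-width = t(0.975, n − 1) × SD/√n = 2.093 × 0.1/√20 = 0.0468, which rounds to 0.05. With one patient lost: 2.101 × 0.1/√19 = 0.0482. Precision hardly changes.

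**Shift in the mean.** Suppose 19 patients average m and the lost patient would have scored m + d (higher logMAR is worse). The full mean is m + d/20 and the observed mean is m, so the result looks better by d/20. The deficits d are assumptions.

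| d (logMAR) | Shift d/20 | Share of 0.0468 |
|---|---|---|
| 0 (non-visual, or binocular acuity preserved) | 0 | 0% |
| 0.1 | 0.005 | 11% |
| 0.2 | 0.010 | 21% |

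**Before the fact.** With a per-patient rate p of such an event, the expected number lost is 20p and the expected shift is (20p/20) × d = p × d. Assume p = 1% to 2% and d = 0.2: 0.01 × 0.2 = 0.002 and 0.02 × 0.2 = 0.004 logMAR, or 4% to 9% of 0.0468. The chance of at least one such patient is 1 − 0.99^20 = 18% to 1 − 0.98^20 = 33%.

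**Other summaries.** Section 10.2 also reports extremes and category percentages. Losing the only patient in the worst QUVID category would change 1/20 = 5% to 0/19 = 0%.

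**The case against.** The best reply is that the gap will rarely matter. The severity definitions (numbered 12.3.1, within section 13) make a severe event an incapacitating one, and it must also be possibly related. Eyes with complicated surgery are already outside the efficacy set under 10.1. To bias the primary outcome, the event must be visual, last to 3 months, reduce binocular acuity, and occur early enough to prevent Visit 6. The exit examination and the monocular visits leave some data. All of this stands, and it keeps the point minor. It does not supply a planned 3-month value.

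A reader might infer that a bad result would be hidden, or that all data on the patient would be lost. The documents do not support either. Safety covers every enrolled subject (10.1), ocular events are tabulated by type, severity, duration and frequency (13.5), and 18.3 requires the termination to be documented. The event would be visible; only the 3-month acuity and questionnaire values would be missing.

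The completion conflict can be called a drafting inconsistency, and 18.3 could even be read as bringing the available data into 10.2. That is fair: the conflict shows no bias. It still leaves the analyst to choose, after seeing the data, whether exit values count.

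**Conclusion.** The concern holds as a minor point. Followed as written, 18.3 and 18.5 can remove the 3-month primary and patient-reported outcomes of a patient terminated before day 70. When the event is visual and persistent, the loss favours the lens.

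The size is unknown, because the documents give neither a severe-event rate nor an acuity deficit. On the assumptions above, one such patient shifts the mean by 0.005 to 0.010 logMAR, the expected shift before the fact is 0.002 to 0.004, and non-visual events give zero. A reader might infer that the primary result would be materially biased. That would need a much larger assumed deficit (0.5 logMAR gives 0.5/20 = 0.025), and nothing in the documents supports one.

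The contradictory completion status rests on the text alone and needs no assumption.

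**What to change.** - **18.3:** a patient with a severe, possibly related event is treated as the investigator judges and stays in follow-up. The Visit 6 assessments are collected in the 90 ± 20 day window unless the patient withdraws consent or the investigator records that testing is unsafe. Delete the statement that these patients count as having completed, so that 18.1 is the only definition of completion.
- **18.5:** the study is complete when every enrolled patient has completed Visit 6 or has exited for any documented reason, including death, withdrawal, loss to follow-up, discontinuation under 18.2 or 9.5, or testing recorded as unsafe. The list must stay open, or some exits would leave the study formally unfinished.
- **10.2:** include these Visit 6 data for patients in the 10.1 efficacy set. Report exit values as exit values, not as 3-month values. State the number missing, with reasons.

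The cost is a short amendment to three sections and a little more analysis work. No visit or procedure is added to those already scheduled. The results may look slightly less favourable.

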10.2. Statistical Methodology

A summary of the data will be prepared for all measurement time points. Summaries of the changes observed between the 1 month and 3 month post-operative visits will also be summarized.

For variables measured on a continuous scale, these summaries will include the sample size, as well as the mean, standard deviation, median, minimum, and maximum. For variables measured on a categorical scale, summaries will provide the number and percentage of subjects who provided each score (or change in scores). These summaries will be provided for all eyes completing the study.

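### Section 18.3 counts a patient terminated for a severe, possibly related adverse event as a completer, while the Exit CRF records non-completion before Visit 6; separately, Sections 10.1 and 10.2 define different sets of eyes for every early exit

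*Combined protocol and SAP*

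**What the plan says.** Section 18.3 sets the trigger, "A study patient will be terminated if the study patient develops any severe adverse event that may be related to the study", and then the status: "These study patients are considered to have completed the study and will not be replaced". It puts no condition on whether Visit 6 has taken place.

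For a premature exit, Section 9.2.7 has the Exit CRF filled in, "noting that the subject did not complete the study and the reason for premature study exit". The footnote to Table 15.1 makes that form due at termination if this precedes Visit 6. Section 9.5 classes as discontinued those "who come into the office to be exited prior to the scheduled final study visit", and lists an adverse event among the reasons. Section 18.1 treats a patient who has done Visit 6 as having completed. Section 18.5 closes the study once every patient has either done Visit 6 or been terminated.

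On analysis sets, Section 10.1 states: "Efficacy analyses will be performed based on data from those eyes where uncomplicated cataract surgery with Vivity IOL implantation was completed". Section 10.2 states: "A summary of the data will be prepared for all measurement time points". It then adds: "These summaries will be provided for all eyes completing the study".

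**The concern.** There are two separate problems.

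The first is status. A patient terminated at, say, the 1-month visit is a completer under 18.3 and a non-completer on the Exit CRF completed at termination. No passage says which prevails. Following 18.3 literally, a safety-related exit is reported as a completed follow-up.

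The second is the analysis set. Section 10.1 keeps every eye with uncomplicated surgery and the study lens, whether or not the subject stayed to the end. Section 10.2 covers all visits but restricts them to completers. For any subject who leaves early, including one lost to follow-up or withdrawing, the two sections disagree on whether the 1-day, 1-week and 1-month data are summarised. The 18.3 label bears on this for terminated subjects only, and only if 10.2 is followed.

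Two analysts could both follow the document and report different denominators. That is better settled before data are seen.

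**Working it through.** **Inputs.** 20 subjects and 40 eyes (Section 7.1). SD 0.1 logMAR and a two-sided 95% t-interval with half-width 0.05 (Section 11). Visit 6 at 90 (±20) days, that is day 70 to day 110 (Table 9.2-1). The documents give no rate for such terminations, so the number of terminated patients, k, is an assumption.

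**The plan's own figure.** Half-width = t(0.975, 19) × 0.1/√20 = 2.093 × 0.1/4.472 = 0.0468, which rounds to the stated 0.05. It serves here only as a yardstick.

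**Status of a patient terminated before Visit 6.**

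| Section | Status given | Against 18.3 |
|---|---|---|
| 18.3 | Completed, not replaced | – |
| 9.2.7 with Table 15.1 footnote | Did not complete; reason recorded at termination | Direct contradiction |
| 9.5 | Discontinued | Conflict of labels |
| 18.1 | Visit 6 done is sufficient for completion; not stated to be necessary | Fits 9.2.7 better; no strict contradiction |
| 18.5 | Termination listed as an alternative to doing Visit 6 | Fits 9.2.7 better; no strict contradiction |

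**Completion count, all other subjects completing.** Under 18.3 it is 20/20 = 100% for any k. Under 9.2.7 it is (20 − k)/20: 19/20 = 95% for k = 1 and 18/20 = 90% for k = 2.

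**Eyes in an earlier-visit summary, k = 1.** Assume both eyes had uncomplicated implantation and the visit was attended.
- Section 10.1 followed: 40 eyes, whatever the label.
- Section 10.2 followed with the 18.3 label: 40 eyes.
- Section 10.2 followed with the Exit CRF status: 40 − 2 = 38 eyes.

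**Shift in an earlier-visit mean from dropping those two eyes.** Assume that the SD of 0.1 applies at that visit and that both eyes lie z SDs from the mean of the 40. Shift = z × 0.1 × 2/38 = z × 0.1/19.
- z = 0 (typical patient): 0.
- z = 1: 0.0053 logMAR, which is 0.0053/0.0468 = 11% of the half-width.
- z = 1.867 (expected largest of 20 standard normal values): 0.0098 logMAR, which is 0.0098/0.0468 = 21% of the half-width.

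**3-month means.** A patient with no Visit 6 value adds nothing under either status, so the label's effect is 0. The same holds for the 1-month to 3-month change in Section 10.2, which needs both values. This fails only if an exit examination done before day 70 were pooled into the 3-month results.

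**The case against.** The strongest reply is that Section 18 deals with study closure and replacement, so 18.3 is an administrative deeming rule: do not replace these patients and do not wait for them. Section 18.1 leaves room for that, because it does not say that Visit 6 is the only route to completion. The reading does not remove the conflict. Non-replacement needs no completed status, Section 18.5 already closes the study on termination, and the Exit CRF instruction still says the opposite.

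More of the reply stands on materiality. The plan commits to no completion rate or disposition table, so the percentages matter only if a completion count is reported. The true status is still captured, on the Exit CRF and through the documentation of termination that 18.3 requires. The named outcomes are set at 3 months or scheduled only at Visit 6, so the earlier-visit summaries serve none of them. The 10.1 and 10.2 mismatch would remain if 18.3 were deleted. Under 10.2, the 18.3 label actually keeps these eyes in.

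A reader might infer that 18.3 hides adverse events. It does not. All enrolled subjects are in the safety evaluation (10.1), every event is recorded (13.3), and ocular events are tabulated (13.5). A reader might also infer that the rule biases the primary outcome. The label cannot move a mean to which the patient contributes no value. Loss of Visit 6 data after a termination is a separate matter. It need not be related to visual outcome, since an incapacitating event may be non-ocular, and Section 9.2.7 already asks that "all study related examinations should be completed where possible".

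**Conclusion.** The point holds, as a minor one. Section 18.3 directly contradicts 9.2.7 with the Table 15.1 footnote for a patient terminated before Visit 6. Sections 18.1 and 18.5 lean towards 9.2.7, but the documents do not support saying that they contradict 18.3 outright. Nor do they support saying that 18.3 by itself determines who is analysed. That follows only if 10.2 prevails over 10.1, which the plan does not settle.

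Per such patient, a reported completion count differs by 1 of 20 (100% against 95%). Earlier-visit summaries hold 40 or 38 eyes, and an earlier mean moves by 0 to about 0.01 logMAR. The 3-month means do not move, provided no exit value from before the 90 (±20) day window is pooled into them. These sizes assume an SD of 0.1 at the earlier visits, both eyes equally far from the mean, and at least one such termination before Visit 6. No probability is claimed for that event.

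**What to change.** Adopt both parts together.

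1. Reconcile 18.3 with 9.2.7, 9.5, 18.1 and 18.5, so that only subjects with Visit 6 done are counted as completers. Report terminated subjects as non-completers with the reason; they are still not replaced.
2. In 10.2, replace the restriction to completers with all eyes in the Section 10.1 efficacy set that have data at the visit concerned, and show n at each visit.

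Part 1 alone would make things worse for the analysis: with 10.2 unchanged, reclassifying terminated subjects as non-completers would drop their earlier-visit eyes. Part 2 also settles the question for every other early exit.

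The cost is wording only, plus a slightly less favourable completion figure if such an exit occurs. Sample size, visit schedule and follow-up are unchanged, and no view is taken on when a patient should be terminated.

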18.4. Study Termination

The investigator with appropriate notification may terminate the study. If, after clinical observations, the investigator feels that it may be unwise to continue the study, he may stop the study.

18.5. Study Completion

The study will be complete when all enrolled patients have completed Visit 6 or have been terminated from the study.

19. SUMMARY OF RISKS AND BENEFITS

19.1. Summary of risks

The risks with this study are similar to those for any patient electing for EDOF or multifocal IOLs.⁴⁻⁷ There is no increased risk associated with the proposed study.

